8.2 UNANTICIPATED PROBLEMS

8.2.1 DEFINITION OF UNANTICIPATED PROBLEMS

This protocol uses the definition of Unanticipated Problems as defined by the Office for Human Research Protections (OHRP). OHRP considers unanticipated problems involving risks to participants or others to include, in general, any incident, experience, or outcome that meets all of the following criteria:

- Unexpected in terms of nature, severity, or frequency given (a) the research procedures that are described in the protocol-related documents, such as the Institutional Review Board (IRB)-approved research protocol and informed consent document; and (b) the characteristics of the participant population being studied;
- Related or possibly related to participation in the research (“possibly related” means there is a reasonable possibility that the incident, experience, or outcome may have been caused by the procedures involved in the research); and
- Suggests that the research places participants or others at a greater risk of harm (including physical, psychological, economic, or social harm) than was previously known or recognized.]

8.2.2 UNANTICIPATED PROBLEMS REPORTING

The investigator will report unanticipated problems (UPs) to the reviewing Institutional Review Board (IRB) and to the DSMP/lead principal investigator (PI). The UP report will include the following information:

- Protocol identifying information: protocol title and number, PI's name, and the IRB project number
- A detailed description of the event, incident, experience, or outcome
- An explanation of the basis for determining that the event, incident, experience, or outcome represents an UP
- A description of any changes to the protocol or other corrective actions that have been taken or are proposed in response to the UP.

9 STATISTICAL CONSIDERATIONS

9.1 STATISTICAL HYPOTHESES

Specific Aims:

1. To develop **BREATHE-Peds** in a pediatric population (dyads of caregivers and their 10- to 14-year-old early adolescents with uncontrolled asthma) receiving asthma care in FQHCs;
2. To evaluate the feasibility and acceptability of intervention procedures; and
3. To assess intervention effects on asthma outcomes (monthly x 3 months post-intervention).

Hypotheses:

1. The intervention will be feasible and acceptable as evidenced by: high rates of dyad recruitment and retention; PCP fidelity to the intervention protocol; and PCP and caregiver-child dyad satisfaction.
2. Over 3-months post-intervention, relative to controls, **BREATHE-Peds** children will have improvement (a) in asthma control as measured by the Asthma Control Questionnaire (primary outcome), higher perceived SDM, and (b) on other asthma outcomes (secondary outcomes), including quality of life, school absences, lung functioning, and exacerbation.

MEASURES / ENDPOINTS.

Primary Outcomes: asthma control as measured by improvements in Asthma Control Questionnaire (ACQ) score.

Secondary outcomes: (a) shared-decision-making as measured by scores the Shared Decision-making Questionnaire – 9 items, (b) Self-management as measured by the Medication Adherence Report Scale – Asthma (MARS-A), (c) asthma and ICS beliefs as measured by the Conventional and Alternative Management for Asthma, (d) asthma quality of life as measured by the Pediatric Asthma Quality of Life Questionnaire (PAQLQ) and Pediatric Asthma Caregiver's Quality of Life Questionnaire; and significantly lower rates of (e) asthma exacerbations, (f) symptoms days, (g) nights woken, (h) activity limitations, (i) shortness of breath, (j) wheeze, and (k) rescue medicine use. We will also track Asthma Impairment and Risk questionnaire and Asthma Responsibility Questionnaire scores over time.

Other measures: (1) demographics (age, sex); (2) health literacy as measured by the Newest Vital Sign and the Short Assessment of Health Literacy-English and Spanish; (3) asthma history and (4) lung function as measured by spirometry (COVID permitting).

9.2 SAMPLE SIZE DETERMINATION

Power & Sample Size. With a sample size of 10 patients/PCP and 4 PCPs in each intervention arm (total $n=10*4*2=80$), and 20% attrition, we calculated the power to test the effect of intervention on outcomes. Power calculations were based on: (1) 4 repeated observations over the 3-month follow-up with a correlation of $p=0.8$ between repeated measures; (2) intra-cluster correlation among PCPs=0.2 to account for clustering of patients from the same PCP; and (3) LMMs to estimate pre- and post-intervention differences. We estimated an 80% power to detect a small effect size ($d=0.15$). For ACQ, this is equivalent to detect a post-intervention difference of 0.15 (assuming $SD=0.9$).

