2. Over 3-months post-intervention, relative to controls, **BREATHE-PEDS** children will have improvement (a) in asthma control as measured by the *Asthma Control Questionnaire*⁶³⁻⁶⁵ (primary outcome), higher perceived SDM, and (b) on other asthma outcomes (secondary outcomes), including quality of life, school absences, lung functioning, and exacerbation.

Endpoints:

NAME: Asthma Control Questionnaire
TYPE: Primary
TIME FRAME: Focus groups, Baseline and 1-, 2-, and 3-months post intervention

DESCRIPTION: 6-item validated and widely used measure of asthma control
WHO COMPLETES: Child with help from caregiver as needed

NAME: Shared Decision-Making Questionnaire— 9 items
TYPE: Secondary
TIME FRAME: Focus groups, Immediately after the medical visit (i.e., immediate post-intervention)
DESCRIPTION: 9-item validated measure of the decisional process in medical visits from both patients' and physicians' perspectives
WHO COMPLETES: Child AND Caregiver (PATIENT version) and PCP (clinician version)

NAME: Medication Adherence Record Scale-Asthma
TYPE: Secondary
TIME FRAME: Focus groups, Baseline and 1-, 2-, and 3-months post intervention
DESCRIPTION: 10-item validated measure of inhaled corticosteroid adherence (ICS) (dichotomized as high or not). Scores have been shown to predict Self-management as measured by objective electronic monitoring and prescription refill rates.
WHO COMPLETES: Child with help from caregiver as needed

NAME: Conventional and Alternative Management for Asthma
TYPE: Secondary
TIME FRAME: Focus groups, Baseline and 3-months post intervention
DESCRIPTION: 17-item validated measure of erroneous asthma management beliefs (9 items) and ICS beliefs (8 items)
WHO COMPLETES: Child with help from caregiver as needed AND Caregiver

NAME: Pediatric Asthma Quality of Life Questionnaire
TYPE: Secondary
TIME FRAME: Focus groups, Baseline and 1- and 3-months post intervention
DESCRIPTION: 23 questions in 3 domains (symptoms, activity limitation and emotional function). The activity domain contains 3 'patient-specific' questions. Children are asked to think about how they have been during the previous week and to respond to each of the questions on a 7-point scale (7 = not bothered at all - 1 = extremely bothered). The overall PAQLQ score is the mean of all 23 responses and the individual domain scores are the means of the items in those domains
WHO COMPLETES: Child with help from caregiver as needed

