Intervention Effects. Intervention effects will be assessed using linear mixed models (LMM) and generalized linear mixed models (GLMM) for continuous and categorical outcomes, respectively¹³². All hypothesis tests will be two-sided at level $\alpha=0.05$. The key outcome will be ACQ⁶³⁻⁶⁵ score; secondary measures will be examined to inform the future RCT. Separate models will be fitted for different outcome measures. If y_{ijt} is the outcome for patient j of provider i at time t , without loss generality then the following LMM will be used: $y_{ijt}=\beta_0+\beta_1*Group+\beta_2*t+\beta_3*INT+\beta_4*X_{ij}+\mu_i+\mu_{ij}+\epsilon_{ijt}$, where group, t , and INT are design variables. Group is an indicator for intervention arm and INT is an indicator for pre- or post-intervention. X_{ij} is a vector of possible PCP- and patient-level covariates. The random term $\mu_i \sim N(0, \sigma_1^2)$ is a PCP-specific random effect and $\mu_{ij} \sim N(0, \sigma_2^2)$ is a patient-specific random effect; $\epsilon_{ijt} \sim N(0, \sigma_\epsilon^2)$ is the model random error. To examine the effect of intervention on the outcome, we will conduct hypothesis test of $H_0: \beta_3=0$. We will explore differential intervention effect by sex (early adolescent and/or caregiver) and conduct exploratory analyses to determine if seasonality or differences in disease severity¹⁰⁸ between groups provide alternative explanations for findings.

Power & Sample Size. With a sample size of 10 dyads/PCP and 4 PCPs in each intervention arm (total n=10*4*2=80), and 20% attrition, we calculated the power to test the effect of intervention on ACQ. Power calculations were based on: (1) 4 repeated observations over the 3-month follow-up with a correlation of $\rho=0.8$ between repeated measures; (2) intra-cluster correlation among PCPs=0.2 to

account for clustering of patients from the same PCP; and (3) LMMs to estimate pre- and post-intervention differences. We estimated an 80% power to detect a small effect size ($d=0.15$). For ACQ, this is equivalent to detect a post-intervention difference of 0.15 (assuming $SD=0.9$).

Qualitative Data. Two or three coders will independently perform conventional content analysis¹³³. To enhance rigor, we will use multiple data sources (credibility), rich contextual descriptions (transferability), codebook and saturation tables (dependability) and audit trail (confirmability)¹³⁴⁻¹³⁷. NVivo 12 will manage data.

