9.4.2 ANALYSIS OF THE PRIMARY AND SECONDARY ENDPOINT(S)

Analytic Plan.

Aims 1 & 2: Development and Intervention Feasibility. We will document our success in meeting recruitment and randomization goals, as well as process (recruitment outreach and numbers meeting eligibility criteria who accept or decline enrollment) and implementation assessments (retention rates, data completion rates, as well as fidelity, contamination and masking in the clinical trial arm).

Randomization. This is a group-randomized trial in which the primary care providers (PCPs) will be randomized within sites to the active and control conditions. We will utilize a stratified block randomization plan, stratifying by provider type (physician vs. nurse practitioner/physician assistant), to insure equal numbers of PCPs within each PCP type are assigned to each condition. Randomization lists will be computer-generated in advance by our biostatistician. Outcomes will be analyzed at the level of the early adolescent and/or caregiver.

Masking. Participants and data collectors will be masked to study hypotheses and group assignment; the investigators will be blinded to group assignment. PCPs in both intervention conditions will use tablets as part of their respective interventions and have sessions audio-recorded, facilitating masking of participants and data collectors.

Aim 3: Intervention Effects. Intervention effects will be assessed using linear mixed models (LMM) or generalized linear mixed models (GLMM) for continuous and categorical outcomes, respectively. All hypothesis tests will be two-sided at level $\alpha=0.05$. The key outcome will be ACQ score; secondary measures will be examined to inform the future RCT. Separate models will be fitted for different outcome measures. If y_{ijt} is the outcome for patient j of provider i at time t , without loss generality then the following LMM will be used:

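### Section 9.2 states 80% power at d = 0.15 for outcomes in general, but its inputs cannot apply to SDM-Q-9, which is taken once after the visit and has about 6–10% power at that effect

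*Combined protocol and SAP*

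**What the plan says.** The power paragraph appears twice. In Section 4.1 it reads "we calculated the power to test the effect of intervention on ACQ". In Section 9.2, the formal sample-size section, the corresponding words are "we calculated the power to test the effect of intervention on outcomes". There 80% power at d = 0.15 is the general result, and ACQ enters only in the closing sentence, as a translation into scale points.

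Both versions use the same inputs. Section 9.2 lists them as "With a sample size of 10 patients/PCP and 4 PCPs in each intervention arm (total $n=10*4*2=80$), and 20% attrition"; "4 repeated observations over the 3-month follow-up with a correlation of $p=0.8$ between repeated measures"; an intra-cluster correlation among PCPs of 0.2; and mixed models of pre-post differences. Section 9.4.2 sets every test two-sided at 0.05.

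For SDM-Q-9, the Section 1.1 endpoint list gives the trial time point as "Immediately after the medical visit (i.e., immediate post-intervention". The schedule table in Section 8 marks only the immediate post-visit column. The endpoint list also names the focus groups, but Section 5.2 bars focus-group participants from the pilot, so these cannot supply a baseline for trial dyads.

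Sections 1.1, 3 and 9.1 class SDM-Q-9 as secondary. Hypothesis 2(a) also names perceived SDM: "primary outcome), higher perceived SDM, and (b) on other asthma outcomes (secondary outcomes". No other power statement covers it.

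**The concern.** The two sections disagree on what was powered, and the wider version is in the section that a reader would consult. Taken at its word, Section 9.2 covers an outcome for which none of its precision-gaining inputs exists: there is no pre value, no repeat and no within-child correlation. The Section 9.4.2 model shows the same mismatch. Its tested term is a pre/post indicator, which takes a single value when every score is post-visit.

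Perceived SDM is what the intervention sets out to change, and Section 9.4.2 says that secondary measures will inform the future RCT. At stake is whether the sensitivity printed in the plan for that measure is one the design has.

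**Working it through.** **Inputs from the documents.** 4 PCPs per arm and 10 dyads per PCP (8 after 20% attrition), PCP ICC 0.2, two-sided 0.05, and d = 0.15 (Sections 9.2 and 9.4.2). **Assumptions.** The ICC of 0.2 is carried over to SDM-Q-9 and varied down to 0. One score per dyad is compared between arms without covariates. Total SD is set to 1, so no SD is needed. The main case has no attrition, because the score is taken at the visit.

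**1. The plan's own figure.** For 80% power at d = 0.15 (normal reference) the SE of the arm difference must be 0.15/2.80 = 0.054. Using the ACQ inputs, with 10 dyads per PCP and normal power:

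- Mean of four values, ICC 0.2. The variance splits as 0.2 PCP, 0.6 child and 0.2 residual. SE = sqrt{(2/4)[0.2 + (0.6 + 0.2/4)/10]} = 0.364; power 7.0%.
- Change from baseline to the mean of three follow-ups, with design effect 1 + 9(0.2) = 2.8. SE = sqrt[(2/40)(2.8)(0.2)(4/3)] = 0.193; power 12.1%.
- Baseline-adjusted mean of three follow-ups, same design effect. The variance factor is (1 + 2×0.8)/3 − 0.8² = 0.227. SE = 0.178; power 13.4%.
- The last two without the design effect: 25.5% and 29.1%.

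A value near 80% appears only with formulas that are not a clustered between-arm test. For example, a variance of 2(1 − 0.8)/(4n), which drops clustering and between-child variance, gives 79% at 68 dyads in total and 81% at 72. So the stated 80% does not reproduce, even for ACQ.

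**2. SDM-Q-9: one post-visit score, no baseline.** With m dyads per PCP,

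Var(difference) = 2[1 + (m − 1)ICC]/(4m).

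For m = 10 and ICC 0.2: 2(2.8)/40 = 0.140, so SE = 0.374 and 0.15/0.374 = 0.40. Power is 6.9% (two-tailed normal) or 6.3% (noncentral t, 8 − 2 = 6 df). The effect detectable with 80% power is 2.80 × 0.374 = 1.05 or 3.37 × 0.374 = 1.26. A simulation of 200,000 trials, analysed by a t-test on PCP means, gave 6.4%.

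| ICC (m = 10) | SE | Power at d = 0.15, normal / t | Detectable d at 80%, normal / t |
|---|---|---|---|
| 0 | 0.224 | 10.3% / 8.8% | 0.63 / 0.75 |
| 0.05 | 0.269 | 8.6% / 7.6% | 0.75 / 0.91 |
| 0.1 | 0.308 | 7.8% / 7.0% | 0.86 / 1.04 |
| 0.2 | 0.374 | 6.9% / 6.3% | 1.05 / 1.26 |

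With m = 8 and ICC 0.2: SE 0.387, power 6.7% / 6.3%, detectable d 1.09 / 1.30. With 85 dyads and ICC 0.2, power is 6.4% to 6.9%. Section 9.2's ACQ translation (0.15 points, SD 0.9) is really d = 0.15/0.9 = 0.167; at that value power is 6.7% to 7.3%.

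**3. Where the shortfall comes from (ICC 0.2, normal power).**

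- One value instead of four: SE 0.374 against 0.364, power 6.9% against 7.0%. This is almost nothing.
- Unlimited dyads per PCP: SE = sqrt(2 × 0.2/4) = 0.316, power 7.6%. Eight PCPs set the ceiling.
- A baseline, as in step 1: 12% to 13%. This is the gain that SDM-Q-9 forgoes.

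**The case against.** Section 9.2 never names SDM-Q-9. Its own conditions (four observations, pre-post differences) describe a repeated measure, ACQ is the only outcome it quantifies, and Section 9.4.2 calls ACQ the key outcome. The plural may well be a loose edit of Section 4.1. That is fair, and it makes this a problem of scope rather than an express claim about SDM-Q-9. It is nevertheless the current text of the sample-size section, it conflicts with Section 4.1, and nothing else limits it.

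A second objection is that most of the gap between 80% and 6–7% belongs to the power calculation as a whole. This also stands: step 1 shows ACQ falling far short too. The part peculiar to SDM-Q-9 is that the inputs cannot apply to it at all, so recalculating the ACQ figure would not settle the matter.

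Third, child and caregiver both complete the measure and the model allows covariates, so one unadjusted score per dyad may be pessimistic. Neither rescues the claim. Even at ICC 0, the variance would have to fall from 0.050 to about 0.0029 (0.0535²), a cut of some 94%.

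Some stronger readings are tempting but unsupported. A reader might infer that the design can detect only effects of about one SD or more; that depends on borrowing the ICC of 0.2, and the figure is 0.63 to 0.75 at ICC 0. A reader might take the placing of perceived SDM in Hypothesis 2(a) as co-primary status; the endpoint lists class it as secondary. A reader might also infer that the sponsor will treat a null SDM-Q-9 result as no effect; no section says so.

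**Conclusion.** The point holds as a mismatch of scope with a numerical consequence. Section 9.2 states a power for outcomes in general that the design does not have for SDM-Q-9. At d = 0.15 the power is 6–7% if the plan's ICC of 0.2 carries over, and 9–10% if there is no clustering at all. The detectable effect runs from 0.63–0.75 (ICC 0) to 1.05–1.26 (ICC 0.2), roughly 4 to 8 times the printed 0.15. The ICC is an assumption, but no value from 0 to 0.2 brings power anywhere near 80%.

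The main causes are the eight PCPs and the absence of a baseline; the single measurement as such matters little. Nothing here implies that ACQ does have 80% power. The importance is moderate: this is a feasibility trial, SDM-Q-9 is secondary, and no sample-size choice rests on it. The statement should still be corrected.

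**What to change.** In Section 9.2:

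1. Limit the power statement to ACQ, matching Section 4.1. Do not carry the 80% forward as confirmed; the ACQ calculation must be redone separately, showing the formula and how the ICC enters.
2. State that the calculation does not cover outcomes without a baseline or repeated measures.
3. For SDM-Q-9, give the detectable effect at 80% power for a single post-visit comparison with 4 PCPs per arm and 10 dyads per PCP, as a range over the assumed ICC: about d = 0.63–0.75 at ICC 0, rising to 1.05–1.26 at ICC 0.2 (normal to t with 6 df). Say that the ICC is assumed.

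Optionally, in Section 9.4, say that SDM-Q-9 will be reported as an arm difference with a 95% interval. This is good practice for a pilot rather than a correction of an error.

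The cost is wording in Section 9.2, and one line in Section 9.4 if the option is taken. No participants, visits or procedures are added. The downside is that the stated sensitivity for SDM-Q-9 becomes much less favourable.

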Asthma's impact is significant among minority populations. Erroneous beliefs impede asthma control. To date, community-based asthma interventions have not reduced the burden of asthma. For this reason, we adapted an evidence based brief SDM intervention used in acute care settings to FQHC settings with input from black adult asthma patients and their loved ones. We will develop this intervention by adapting our prior work in our adults which found several positive short-term effects on asthma control, SDM, and symptom burden.

Pregnant women will be eligible to participate since improving asthma control for their early adolescent children would benefit the family.

Retention of patient participants

UHP has retained 72-90% of participants in clinical trials requiring data collection of 12 months (Personal communication, [name]). To retain 80% of dyads over 3 months post-intervention for this trial, we will use the retention strategies proven successful in our previous trials in FQHCs requiring 3+months of follow-up:

1. Assigning one Research Assistant (RA) to a dyad: Data collection by RAs that have a history of working at these FQHCs will facilitate rapport and retention. RAs are often members of the community; all have received training on the delivery of patient-centered care.
2. Confirming contact information at each assessment; obtaining contact information of two or more people who will know how to contact the participant: We will update contact information (e.g., name, address, phone numbers, emails) for the participants and two or more of their contacts at each study visit; participants will be asked to indicate preferred mode of communication (email, text or phone).
3. Frequent data collection points: There are 4 assessment points over the 3-month follow-up. Participants will receive monthly communication from our study team to confirm upcoming visits. If they fail to respond after three attempts using multiple modes of contact over varying day/evening hours and weekday/weekend attempts, we will contact their alternative contacts.
4. Graduated incentives: Participants will be compensated using a graduated incentive plan. We will pay the dyad: baseline=\$25; 1-month=\$30; 2-month=\$40; 3-month=\$50 (total \$145). A portion of each incentive will be made directly to the child.

Retention of PCP participants

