9.4 STATISTICAL ANALYSES

9.4.1 GENERAL APPROACH

Participants will be described with respect to baseline characteristics (e.g., means, standard deviations, ranges, etc.) Descriptive data analysis will precede formal hypothesis testing to understand the data distribution and to check for outliers to determine the need for transformations of variables or special analytic techniques. We will also examine the patterns of missing data paying special attention to the balance of missing data in the study arms; linear and generalized linear mixed models provide unbiased estimates for data with missing at random when likelihood of missing is not related to the missing data and can be fully accounted for by variables where there is complete information. Intention-to-treat analyses will be conducted which requires data to be analyzed as randomized, regardless of whether participants completed some or none of the intervention. Based on our feasibility trial and the high retention rate in our previous trials, we anticipate 90% will provide baseline, 1-, 2-, and 3-month data.

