$y_{ijt} = \beta_0 + \beta_1 * \text{Group} + \beta_2 * t + \beta_3 * \text{INT} + \beta_4 * X_{ij} + \mu_i + \mu_{ij} + \varepsilon_{ijt}$, where group, t , and INT are design variables. Group is an indicator for intervention arm and INT is an indicator for pre- or post-intervention. X_{ij} is a vector of possible PCP- and patient-level covariates. The random term $\mu_i \sim \text{N}(0, \sigma_1^2)$ is a PCP-specific random effect and $\mu_{ij} \sim \text{N}(0, \sigma_2^2)$ is a patient-specific random effect; $\varepsilon_{ijt} \sim \text{N}(0, \sigma_\varepsilon^2)$ is the model random error. To examine the effect of intervention on the outcome, we will conduct hypothesis test of $H_0: \beta_3 = 0$. We will explore differential intervention effect by sex.

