The consent form includes HIPAA authorization. Copies of signed consent form will be secured in electronic form behind the Columbia firewall or in hardcopy in a locked cabinet in a locked office at CUSON. Trained research assistants will answer questions in the same manner as if the consent was being obtained in-person.

COVID-19 CONSIDERATIONS. If social distancing mandates prevent us from obtaining informed consent or study visits/procedures in-person, we will follow an IRB-approved script to obtain oral consent using telephone or secure web-based videoconferencing platform that is HIPAA-compliant, documenting name, date and time of oral consent.

PHASE 2 only. We will use the same IRB approved screening protocol from our prior trials that allowed us to obtain screening data by phone (asthma control score) with an initial verbal consent from the caregiver

and child assent. Those children whose asthma control score indicates that they have uncontrolled asthma will have their baseline visit scheduled within ~14 days. If at any time the children experience a loss of asthma control, they will be told to seek immediate medical attention. Written consent/assent will be obtained as previously described.

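### The stated 80% power at d=0.15 does not hold for the between-arm ACQ comparison; on the plan's own inputs it is about 21–27%

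*Combined protocol and SAP*

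**What the plan says.** Section 9.2, with near-identical text in 4.1, bases power on 80 dyads (10 per PCP, 4 PCPs per arm), 20% attrition, four repeated observations correlated at 0.8, and an ICC of 0.2 by PCP. It concludes: "We estimated an 80% power to detect a small effect size ($d=0.15". For the ACQ it adds that "this is equivalent to detect a post-intervention difference of 0.15 (assuming $SD=0.9".

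The primary hypothesis in 9.1 compares the arms: "Over 3-months post-intervention, relative to controls". Section 9.4.2 sets the test: "All hypothesis tests will be two-sided at level $\alpha=0.05". The model there has main effects for group, time and INT, and tests the INT coefficient. It says that "INT is an indicator for pre- or post-intervention". No group-by-post term is written.

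On the number of observations, 5.4 says: "There are 4 assessment points over the 3-month follow-up". It lists payments at baseline and at 1, 2 and 3 months. The ACQ is also taken at screening (table in section 8). The Phase 2 text in 10.1.1.2 refers to a protocol that "allowed us to obtain screening data by phone (asthma control score".

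On retention, 9.4.1 differs from the 20% attrition in 9.2: "we anticipate 90% will provide baseline, 1-, 2-, and 3-month data".

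**The concern.** All the inputs are stated, so the 80% can be checked. An effect of 0.15 SD is small for 32 analysed dyads per arm, even with a correlation of 0.8. The conversion to ACQ points is also inconsistent with the stated SD.

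ACQ is the named primary outcome, it is tested at 0.05, and the results are meant to inform a later RCT. A reader who believes that 0.15 SD was detectable with 80% power could take a null ACQ result as evidence of no effect. On the stated inputs, the between-arm test would miss an effect of that size roughly three times in four.

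**Working it through.** **Inputs.** From 9.2: 40 dyads per arm less 20% gives n = 32; ICC 0.2; correlation 0.8; SD 0.9. From 9.4.2: two-sided 0.05. From 5.4: four assessments, read as one pre and three post.

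**Variance components**, with total variance 1. The PCP component is 0.2. The residual is 1 − 0.8 = 0.20 if 0.8 is the total correlation between a child's scores. It is 0.8 × 0.2 = 0.16 if 0.8 applies within PCP. The plan does not say which.

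**Conversion.** 0.15 × 0.9 = 0.135 points. In the other direction, 0.15 / 0.9 = 0.167 SD. Both effect sizes are carried below.

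**Trying to reproduce 80%.** The nearest candidate in the text is a before/after contrast pooled over both arms without a time trend, SE = √[residual × (1 + 1/3) / N]. With N = 64:
- Residual 0.20: SE 0.0645, power 64% at d=0.15 and 73% at d=0.167.
- Residual 0.16: SE 0.0577, power 74% and 82%.

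With the linear time term that 9.4.2 includes, these fall to 31–45%. This contrast may explain the 80%, but the plan does not show that it does, and it does not compare arms.

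**Between-arm term.** With random intercepts for PCP and child, both cancel from the group-by-post contrast:

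SE = √[2 × residual × (1/pre + 1/post) / n]; power ≈ Φ(d/SE − 1.96)

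- Residual 0.20: √[2 × 0.20 × (4/3) / 32] = 0.1291. At d=0.15, 0.15/0.1291 = 1.162, so power is 21%; at d=0.167 it is 25%.
- Residual 0.16: √[2 × 0.16 × (4/3) / 32] = 0.1155. Power is 25.5% and 30%.
- Constraining the arms to a common baseline mean (generalised least squares on the 8-PCP design): SE 0.1250 and 0.1125. Power is 22% and 27% at d=0.15, and 27% and 32% at d=0.167.

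A simulation of 20,000 trials (residual 0.20, d=0.15) gave 21.0%.

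**Other readings**

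| Reading | Power |
|---|---|
| Group-by-post, 32 per arm, d=0.15 | 21–27% |
| Same, d=0.167 | 25–32% |
| Lost dyads give partial data (dropout timing assumed), d=0.15 / 0.167 | 22–31% / 26–37% |
| 36 per arm (90% retention), d=0.15 / 0.167 | 23–29% / 28–35% |
| INT read as arm-by-post with a common linear trend, 32 per arm, both d | 28–41% |
| Screening ACQ as a second pre-measure, group-by-post, 32 per arm, both d | 31–45% |
| Screening ACQ added, arm-by-post, 32 per arm, both d | 38–54% |
| Most favourable computed: screening added, 80 dyads, no attrition, residual 0.16, common baseline mean, arm-by-post, d=0.167 | 64% |
| Same, all 85 dyads analysed | 66% |

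Reading the four observations as four post visits adds only one to two points to the first two rows. The screening variants place that score half a month before baseline.

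**Detectable difference at 80% power** (2.80 × SE; points = SD × 0.9):
- 32 per arm: 2.80 × 0.1291 = 0.36 SD (0.33 points); 2.80 × 0.1155 = 0.32 SD (0.29 points).
- 36 per arm: 0.34 SD (0.31 points) and 0.31 SD (0.27 points), from SEs of 0.1217 and 0.1089.

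**Dyads needed for d=0.15 at 80%**: n = 2 × residual × (4/3) × 2.80² / 0.15², which gives 149 (residual 0.16) to 187 (residual 0.20) analysed per arm. With the screening score as a second pre-measure it is 94 to 117.

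**The case against.** The strongest reply is that the 80% is close to what the written test delivers. Section 9.2 speaks of pre/post differences, and 9.4.2 tests a pre/post indicator. The pooled contrast reaches 82% with 64 dyads, a 0.15-point effect and the within-PCP correlation, and 78–79% under some settings with 72 dyads. That stands as a plausible origin of the figure, but only if the time trend in the written model is dropped. It does not rescue the claim, because the contrast says nothing about one arm against the other. It does show that the missing group-by-post term lies behind the power problem, so the two should be corrected together.

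A second reply is that 0.15 SD might be a difference in slope per month, which gives 85%. That would mean 0.45 SD by month 3, whereas 9.2 describes a post-intervention difference of 0.15.

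Third, the replacement figures are themselves optimistic. This is fair. They use z tests and assume that PCPs do not differ in change. With 6 degrees of freedom for eight PCPs, power at d=0.15 is 17–20% and the detectable difference is about 0.39–0.43 SD. Both points make the stated 80% less tenable.

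Fourth, no section says that the screening ACQ enters the model. It is the eligibility score, so regression to the mean is a concern. Those variants serve here only as a generous bound.

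Finally, this is a feasibility trial, where formal power matters less. But the plan itself states power for the intervention effect, names a primary outcome and tests it at 0.05.

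**Conclusion.** The concern holds, with high confidence. The 80% does not apply to the between-arm hypothesis. Power for that comparison is 21–27% at d=0.15, or 25–32% if the effect meant is 0.15 points. These figures rest on 32 analysed dyads per arm, one pre and three post scores, random intercepts only, and the correlation of 0.8 read either way. No between-arm reading of a 0.15 post-intervention difference came above 66%. The detectable difference is more than twice the one stated. The equivalence of d=0.15 and 0.15 points at SD 0.9 is wrong on any reading. The power statement must be corrected, because it is the plan's only quantitative basis for interpreting the primary comparison.

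**What to change.** Keep the sample size. In 4.1 and 9.2:

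- Delete the claim of 80% power at d=0.15.
- Name the group-by-post term as the one powered and tested, and make the model in 4.1 and 9.4.2 agree.
- Insert wording such as: *With 32 analysed dyads per arm (80% retention), baseline and three follow-ups, correlation 0.8, ICC 0.2 and two-sided 0.05, this term has 80% power for a difference of 0.32 SD (0.29 ACQ points; correlation within PCP) to 0.36 SD (0.33 points; total correlation).* If 90% retention is intended, use 0.31–0.34 SD (0.27–0.31 points).
- Say which correlation and which retention apply, and whether the screening ACQ enters the model.
- Note that the detectable difference is larger if PCPs differ in change or if few-cluster degrees of freedom are used.
- Correct the conversion between d and ACQ points.
- Report ACQ effects as estimates with confidence intervals.

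The cost is wording, plus writing the between-arm term into the model. No patients or visits are added. The published figure becomes less favourable.
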